13.2 Analysis Populations

13.2.1 Screened / Randomized Set

The Screened Set will include all patients who signed an informed consent. The Randomized Set will include all patients randomized and will be used for the presentation of patients in all patient listings. Randomized but not treated subjects will be replaced.

13.2.2 Safety Set (SS)

The Safety Set will include all patients who were administered any amount of study medication. Patients will be analyzed according to treatment received. The SS will be used for all analyses of safety endpoints.

13.2.3 Intent-to-Treat (ITT) Set

The Intent-to-Treat (ITT) Set will include all randomized and dosed patients. Replaced subjects will not be included in the ITT. Patients will be analyzed according to randomized treatment. The ITT will be used as primary population for analyses of efficacy endpoints.

13.2.4 Modified ITT

A number of modified ITT (mITT) populations will be defined, as a result of either the COVID-19 pandemic or the conflict in Ukraine.

mITT1: will include all randomized patients who were dosed, except those who discontinue treatment due to a COVID-19 infection as defined in section 12.1.8.7 or do not have at least two SUA measurements 7 days apart in TP6 due to a/multiple missed visits due to a COVID-19 infection or subsequent complications as defined in section 12.1.8.7.

mITT2 will include all randomized patients who were dosed, except those who were recruited in sites from Ukraine or Russia where the data quality are compromised due to logistical issues, defined as:

 Selecta Biosciences	PHASE 3 STUDY: SEL-212/302 VERSION: 7.1	EFFECTIVE DATE 15 DEC 2022
---	--	-------------------------------

4. Those who received fewer than 6 treatment doses due to logistical issues, for example a patient who is unable to receive one or more doses within the 90 day window due to lack of IMP or site closure due to the conflict.
5. Those who have limited laboratory safety data available/reportable after February 24, 2022, for example missing data that result in major protocol deviations
6. Those whose data were not able to be monitored after February 24, 2022

miITT3: will include all randomized patients who were dosed, except those who were recruited in sites from Ukraine or Russia.

Patients will be analyzed according to randomized treatment.

13.2.5 Per Protocol Set

The Per Protocol Set (PPS) will include all patients who were administered at least one complete dose of study medication, who have at least one post-baseline assessment of sUA, who have sufficient data to assess the primary efficacy endpoint, and who have no major Protocol deviations affecting the primary efficacy assessments. Patients will be analyzed according to randomized treatment. Criteria for exclusion from the PPS will be provided in the Statistical Analysis Plan.

13.2.6 All randomized Set

The all randomized set will include all patients who were randomized. Patients will be analyzed according to randomized treatment group assignment

13.3 Protocol Deviations

All protocol deviations related to study inclusion or exclusion criteria, conduct of the trial, patient management, dosing, and sampling procedures or patient assessment will be listed. The list of protocol deviations will be reviewed by the Sponsor, the principal investigator, the study statistician and finalized before database lock.

13.4 Efficacy Analyses

13.4.1 Primary Efficacy

The primary efficacy endpoint is defined as:

- Percentage of patients on SEL-212 versus placebo who achieve and maintain reduction of sUA < 6 mg/dL for at least 80% of the time during Treatment Period 6 by Day 28

The main estimand for the primary efficacy endpoint is defined as follows:

- Targeted population: Of all patients with gout refractory to conventional treatment defined by the study inclusion / exclusion criteria, the analysis population will include patients who were randomized to study treatment and who were dosed (ITT population).

 Selecta Biosciences	PHASE 3 STUDY: SEL-212/302 VERSION: 7.1	EFFECTIVE DATE 15 DEC 2022
--	--	-------------------------------

- Variable: Binary variable indicating the treatment response status, whereby a responder is defined as a patient has sUA < 6 mg/dL for at least 80% of the time during Treatment Period 6.
 - Intercurrent events:
 - Intercurrent events which lead to a discontinuation of study treatment due to lack of efficacy (includes meeting the stopping criteria) will be defined as treatment failures according to the composite strategy.
 - Premature stopping of study treatment due to treatment-related or non-treatment-related AE, with the exception of a positive COVID-19 test result along with severe or critical symptoms of COVID-19 will be defined as treatment failures according to the composite strategy.
 - Premature stopping of study treatment due to a positive COVID-19 test result along with severe or critical symptoms of COVID-19 will be defined as treatment failures according to the composite strategy.
 - Death will be considered as treatment failures according to the composite strategy.
 - Use of prohibited medication that lower sUA levels will be considered as treatment failures according to the composite strategy.
 - All other intercurrent events (e.g. use of prohibited medication that do not lower sUA levels but are classified as a major protocol deviation) will be treated using the treatment policy strategy i.e. the assessment of the sUA in TP6 up to Day 28 will be used..
 - Population-level summary: Difference in the percentage of treatment responders of each SEL-212 treatment group versus placebo.

Further estimands of interest for the primary efficacy will be provided in the SAP.

Frequency table of the treatment responders for the main primary efficacy estimand and further estimands of interest will be provided by treatment group, and the difference between each SEL-212 treatment group and placebo will be presented together with 97.5% confidence intervals.

The statistical testing of each SEL-212 treatment group versus placebo in all estimands of primary efficacy will be performed using the Mantel-Haenszel (MH) estimate and test for common risk difference considering the randomization stratum of tophus presence (yes/no) with a two-sided type 1 error rate $\alpha = 2.5\%$ to adjust for the two comparisons against placebo. Only the test results of the main estimand will be considered as confirmatory.

All above described analyses will be repeated on each of the defined mITT populations, all randomized population and on the PP population as a supportive analysis.

The sUA time curve with assessments at Day 0 pre-treatment (0 h), Day 0 post-treatment (4.5 h), Day 7, Day 14, Day 21, and Day 28 will be used to estimate the proportion of time that the sUA level is below 6 mg/dL. Based on the serum samples collected during Treatment Period 6, an estimate of the time with sUA < 6 mg/dL by Day 28 can be determined by connecting each two neighboring data points with a straight line. If the sUA time curve goes above 6 mg/dL the linear interpolation method will be used to estimate the point in time at which the sUA time curve intercepts the line between the last sUA value < 6 mg/dL and the first value \geq 6 mg/dL. The proportion of time that the sUA level is < 6 mg/dL will be computed by taking the ratio between the time during which the sUA level remains < 6 mg/dL (if necessary, using the linear interpolation method) and the entire time interval within Treatment Period 6 by Day 28, or the last available assessment before Day 28. Actual times will be plotted on the time curve, but only the interpolation of actual times up to Day 28 will be used. If a point at Day 28 is not available on the curve (possibly due to an extension of TP6 for reasons such as presenting mild-moderate COVID-19 symptoms), then the next available assessment between Day 28 and up to, and including EOS will be used to interpolate the curve up to Day 28. This can include the use of unscheduled sUA assessments. If there are no such assessments available, but the use of unscheduled assessments allows the extension of the time curve from the last scheduled assessment prior to Day 28 then these can also be used. If only 2 or fewer assessments are available (allowing for the use of assessments after Day 28 up to, and including EOS, and further unscheduled assessments prior to Day 28), and the first and last attended assessments are less than 7 actual days apart, then the response evaluation of Treatment Period 6 will be missing. Otherwise, the response evaluation will be derived from the available data points.

The proportion of time that the sUA level is < 6 mg/dL, i.e., percentage of non-hyperuricemic time, will be computed by taking the ratio between the time during which the sUA level remains < 6 mg/dL (if necessary, using the linear interpolation method) and the entire time interval within Treatment Period 6 by Day 28 (or last available assessment prior to Day 28 if no assessments are available from Day 28 up to, and including EOS).

For a patient who has completed Treatment Period 6 to be considered a responder, the proportion of time that the sUA level is < 6 mg/dL (i.e., percentage of non-hyperuricemic time) during Treatment Period 6 by Day 28 must be at least 80%.

Frequency table of the percentage of responder in Treatment Period 6 (patients who achieve and maintain reduction of sUA < 6 mg/dL for at least 80% of the time in Treatment Period 6) will be provided by treatment group. Additionally, a summary table with the total time a patient has sUA values < 6 mg/dL in Treatment Period 6 will be provided by treatment group.

Summary table of the actual values and change from baseline for sUA results will be provided for each scheduled sampling time point by treatment group.

Additionally, mean sUA level, reduction in mean sUA and percent reduction in mean sUA from baseline during Treatment Period 6 will be presented by treatment group.

- Mean sUA level is defined as the area under the sUA time curve (computed using the linear trapezoidal rule during Treatment Period 6) divided by the corresponding time interval.
- Reduction in mean sUA is computed by subtracting baseline sUA level from mean sUA during Treatment Period 6.
- Percent reduction in the mean sUA from baseline is computed as the mean sUA level during Treatment Period 6 minus baseline sUA level divided by baseline sUA level multiplied by 100%.

13.4.2 Key Secondary Efficacy

Hierarchical testing of key efficacy:

If the superiority of both (one) SEL-212 treatment group(s) against placebo for the main estimand of the primary efficacy is shown with a p-value ≤ 0.025 , the hierarchical testing approach will continue to the testing of the main estimands of the key secondary efficacy comparing pairwise both (one) SEL-212 treatments against placebo. Only the main estimands of the key secondary efficacy will be tested in the successive order of the key secondary efficacy endpoints listed below. The test result of the nth key secondary efficacy estimand will be considered as confirmatory if the p-value of the two-sided test of the previous estimand resulted in a value less or equal 0.025.

Key secondary efficacy endpoints:

1. Reduction of mean sUA as computed by subtracting the Baseline sUA level from the mean sUA (area under the sUA time curve) during Treatment Period 6
2. Percent reduction of mean sUA as computed by subtracting the Baseline sUA level from the mean sUA (area under the sUA time curve) during Treatment Period 6
3. The change from Baseline to Day 28 of Treatment Period 6 in the physical summary score of the Short Form Health Survey (SF-36)
4. In patients with tophi at Baseline, the percentage of patients at least PR (as best response) in overall tophus response evaluation until Day 28 of Treatment Period TP6
5. The percentage of patients who achieve and maintain reduction of sUA < 6 mg/dL for at least 80% of the time during Treatment Period TP6 by Day 28 in the subset of patients with tophi at baseline
6. The change from Baseline to Treatment Period 6 in number of tender joints
7. The change from Baseline to Treatment Period 6 in the total score of Health Assessment Questionnaire (HAQ-DI)
8. Gout flare incidence during Treatment Periods 1-6
9. Gout flare incidence during Treatment Periods 1-3

The targeted population for all estimands of the key secondary efficacy endpoints numbered as 1, 2, 3, 6, 7, 8, and 9 is the same population as for the primary efficacy. In case of the key secondary efficacy endpoints numbered 4 and 5, the targeted population is additionally restricted to patients with tophi at baseline.

The main estimand for the key secondary efficacy endpoint 'Reduction of mean sUA as computed by subtracting the Baseline sUA level from the mean sUA (area under the sUA time curve) during Treatment Period 6' considers as variables of interest 'absolute difference between mean sUA value recorded in TP6 and the baseline sUA value', whereby the handling of all intercurrent events except death will be according to the treatment policy strategy. For deaths, the last available value will be used (while-on-treatment strategy). The population-level summary is the difference in mean between each SEL-212 treatment group vs. placebo.

The main estimand for the key secondary efficacy endpoint 'Percent reduction of mean sUA as computed by subtracting the Baseline sUA level from the mean sUA (area under the sUA time curve) during Treatment Period 6' considers as variables of interest 'mean TP6 sUA value – baseline sUA value) \div baseline sUA value $\times 100$ ', whereby the handling of all intercurrent events except death will be according to the treatment policy strategy. For deaths, the last available value will be used (while-on-treatment strategy). The population-level summary is the difference in mean between each SEL-212 treatment group vs. placebo.

The main estimand for the key secondary efficacy endpoint 'Change from Baseline to Day 28 of Treatment Period 6 of the Physical Summary Score of SF-36' consider as variable of interest 'Change from Baseline to 6 months after start of study treatment (Day 28 of Month 6)', whereby the handling of all intercurrent events except death will be according to the treatment-policy strategy. For deaths, the last available value will be used (while-on-treatment strategy). The population-level summary is the difference between each SEL-212 treatment group versus placebo in the change from baseline in Physical Summary score of SF-36.

The main estimand for the key secondary efficacy endpoint 'percentage of patients with at least PR (as best response) in overall tophus response evaluation until Day 28 of Treatment Period 6' in patients with tophi at baseline considers as variable of interest the 'binary variable indicating whether the patient had experienced at least a PR or not in overall tophus response evaluation until Day 28 of Treatment Period 6', whereby the handling of all intercurrent events except death will be according to the treatment-policy strategy. For deaths, best response until the last available response evaluation will be used (while-on-treatment strategy). The population-level summary is the difference in the percentage of patients with at least PR in overall tophus response (best response) between each SEL-212 treatment group versus placebo.

The main estimand for the key secondary efficacy endpoint 'percentage of patients who achieve and maintain a reduction of sUA < 6 mg/dL for at least 80% of the time during Treatment Period 6 in a subset of patients with tophi at baseline' considers as variable of interest the 'Binary variable indicating the treatment response when having completed 6 cycles of study treatment, whereby a responder is defined as a patient who has sUA < 6 mg/dL for at least 80% of the time during Treatment Period 6'. All intercurrent events which lead to a discontinuation of study treatment due to lack of efficacy (includes meeting the stopping criteria) treatment-related or non-treatment-related AE, present a positive COVID-19 test result along with severe or critical symptoms of COVID-19, used a prohibited medication that

significantly lowers sUA, or death, will be considered as treatment failures following the composite strategy. All other intercurrent events (e.g., use of a prohibited medication that does not lower sUA) will be treated using the treatment-policy strategy. The population-level summary is the difference in the percentage of treatment responders of each SEL-212 treatment group versus placebo.

The main estimand for the key secondary efficacy endpoint 'change from Baseline to Day 28 of Treatment Period 6 in number of tender joints' considers as variable of interest the 'absolute change in number of tender joints from Baseline to 6 months after start of study treatment (Day 28 of Month 6)', whereby the handling of all intercurrent events except death will be according to the treatment-policy strategy. For deaths, the last available value will be used (while-on-treatment strategy). The population-level summary is the difference in the change from baseline in number of tender joints between each SEL-212 treatment group versus placebo.

The main estimand for the key secondary efficacy endpoint 'Change from Baseline to Day 28 of Treatment Period 6 of the Total Score of HAQ-DI' consider as variable of interest 'Change from Baseline to 6 months after start of study treatment (Day 28 of Month 6)', whereby the handling of all intercurrent events except death will be according to the treatment-policy strategy. For deaths, the last available value will be used (while-on-treatment strategy). The population-level summary is the difference between each SEL-212 treatment group versus placebo in the change from baseline in the Total Score of HAQ-DI.

The main estimand for the key secondary efficacy endpoint 'gout flare incidence in Treatment Period 1 to Treatment Period 6' and 'gout flare incidence in Treatment Period 1 to Treatment Period 3' considers as variable of interest 'Incidence of gout flare during the whole treatment period from start of treatment until end of month 6'. and 'incidence of gout flare during the first 3 months of treatment'. Gout flare incidence is defined as the total number of gout flares a patient experiences in respective time period divided by the length of observation of the patient in this time period. The handling of all intercurrent events except death will be according to the treatment-policy strategy. For deaths, the while-on-treatment strategy will be used. The population-level summary is the difference in the gout flare incidences between each SEL-212 treatment group versus placebo for the whole treatment period (start of treatment until end of month 6) and for the first 3 months of treatment. The analysis will be performed separately for the whole treatment (Treatment Period 1 to Treatment Period 6) and for the first 3 months (Treatment Period 1 to Treatment Period 3). whereby the confirmatory statistical comparison will be performed first for the whole treatment, then for the first 3 months.

Further estimands for the key secondary efficacy will be defined in the SAP.

For the above defined estimands, the key secondary efficacy endpoints which are numbered 1, 2, 8 and 9 will be tested between each SEL-212 treatment group versus placebo using an ANCOVA, adjusting for treatment, randomization stratum and baseline value of the respective variable. The Least Square (LS) Mean difference between each SEL-212 and placebo treatments groups will be estimated along with its 97.5% confidence interval, and 2-sided p-values.

For the above defined estimands, the key secondary efficacy endpoints which are numbered as 3, 6 and 7 above - will be tested between each SEL-212 treatment group versus placebo using the mixed model for repeated measures (MMRM) with the change to baseline in the respective variable as dependent variable, and treatment, treatment-by-period interaction, randomization stratum and baseline value of the respective variable as fixed effect variables. The Least Square (LS) Mean difference between each SEL-212 and placebo treatments groups will be estimated on the treatment-by-period interaction at Treatment Period 6, along with its 97.5% confidence interval, and 2-sided p-values.

For the above defined estimands, the key secondary endpoints numbered as 4 and 5 will be tested between each SEL-212 treatment group versus placebo using the Chi-square test with continuity correction.

The analysis of the estimands will be carried out based on the ITT population with multiple imputation of missing values.

The number of tender joints at scheduled visits and the change from baseline will be summarized by treatment group on the ITT, mITT, all randomized and PP populations.

Frequency table of tophaceous patients at baseline with / without tophus reduction will be provided by visit and treatment group on the ITT, mITT, all randomized and PP populations. Additionally, the time until the first tophus reduction (i.e., the first time CR or PR is assessed in overall tophus response) will be summarized using descriptive statistics by treatment group on the ITT, mITT, all randomized and PP populations.

The HAQ-DI total score and the SF-36 summary score at scheduled visits and the change from baseline will be summarized by treatment group on the ITT, mITT, all randomized and PP populations.

Frequency table of the number and percentage of patients reporting gout flares per 3-months period, will be summarized by period and treatment group on the ITT, mITT, all randomized and PP populations. Additionally, a frequency table of the number and percentage of patients reporting gout flares per 3-month period by severity (life-threatening / severe / moderate /mild) and treatment group will be provided. The number and percentage of patients with at least one life-threatening or severe versus the number and percentage of patients with only mild or moderate gout flares per 3 month period will be presented for each treatment group.

Further supportive analyses for key secondary efficacy variables will be defined in the SAP.

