13.1 Sample Size Determination

The primary efficacy criterion in this study is defined as the percentage of the patients who achieve and maintain reduction of sUA < 6 mg/dL for at least 80% of the time during Treatment Period 6 by Day 28.

The sample size estimation is based on the main estimand for the primary efficacy criterion from version 5.0 of the protocol. This estimand considered all patients who discontinue study treatment due to lack of efficacy (e.g., meeting stopping rule), due to treatment-related or non-treatment related AE as treatment failures, as well as initiating prohibited medication that lowers sUA, withdrawal of consent or lost to follow up for reasons other than COVID-19.

Based on the results in the Phase 2 study (SEL-212/201) with SEL-212, the responder rate in all randomized and dosed patients is assumed to be 45% in SEL-212. For placebo, a responder rate of 5% is assumed. Considering a randomization ratio of 1:1:1 for SEL 212A and SEL-212B against placebo, a statistical power of 90%, a two-sided alpha-level of 2.5% and using the Chi-square test with continuity correction for the 2 pairwise comparisons of each SEL-212 dose group against placebo, 32:32:32 randomized and dosed patients will be required for each treatment group. Considering the potential that some randomized patients will terminate early (approx. 8%), the number of the patients required to be randomized and dosed in total is 105 (i.e., 35:35:35) to demonstrate efficacy. For the sample size estimation, the Chi-square test is used instead of the Mantel-Haenszel test, although the randomization will be stratified for tophus presence (yes/no), as there is no valid assumption of the distribution of this stratification variable within the eligible patient population.

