### 9.3. Key Secondary Efficacy Estimands and Analyses

#### 9.3.1. Hierarchical Testing Approach of Key Secondary Efficacy Estimands

If the superiority of both(one) SEL-212 treatment group(s) against placebo for the main estimand of the primary efficacy is shown with a p-value  $\leq 0.025$ , the hierarchical testing approach will continue to the testing of the main estimands of the key secondary efficacy comparing pairwise both (one) SEL-212 treatments against placebo. Only the main estimands of the key secondary efficacy will be tested in the successive order as defined in Section 6.2. The test result of the  $n^{\text{th}}$  key secondary efficacy estimand will be considered as confirmatory, if the p-value of the two-sided test of the previous estimand resulted in a value less or equal 0.025.

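### The key secondary gate checks only the previous p-value: read literally, a failed sequence can restart at endpoint 6, taking the per-dose error from 2.5% to about 4.3–5.1% if only the sUA endpoints truly respond

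*Protocol*

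**What the plan says.** Each SEL-212 dose is compared with placebo at its own two-sided level of 2.5%. Protocol 13.1 sizes the trial with "a two-sided alpha-level of 2.5% and using the Chi-square test with continuity correction", and the two doses together use 5%.

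Protocol 13.4.2 opens the key secondaries with a condition on the primary: "If the superiority of both (one) SEL-212 treatment group(s) against placebo for the main estimand of the primary efficacy is shown", at p ≤ 0.025. The nine key secondaries then "will be tested in the successive order of the key secondary efficacy endpoints listed below". The ones that matter here are:

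- 1 and 2: absolute and percent reduction in mean sUA
- 3: SF-36 physical summary score
- 4: tophus response
- 5: the primary sUA response, "by Day 28 in the subset of patients with tophi at baseline"
- 6 and 7: tender joints and HAQ-DI
- 8 and 9: flare incidence, ending with "9. Gout flare incidence during Treatment Periods 1-3"

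The rule for moving along the list is that the nth result is "considered as confirmatory if the p-value of the two-sided test of the previous estimand resulted in a value less or equal 0.025". SAP 9.3.1 repeats it: "considered as confirmatory, if the p-value of the two-sided test of the previous estimand resulted in a value less or equal 0.025". The synopsis uses the same condition: "if the p-value of the two-sided test of the previous estimand resulted in a value less or equal 0.025".

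Neither document says that testing stops at the first failure, that the previous result must itself have been confirmatory, or that it must favour SEL-212. SAP 9.3.2 describes a test for each of the nine endpoints and does not make any of them depend on earlier results.

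**The concern.** A fixed sequence needs no further alpha adjustment because a later hypothesis can be claimed only when every earlier one has been rejected. The written condition looks back one step only. An endpoint that is not itself confirmatory, because the sequence broke before it, can still supply the p-value that makes the next endpoint confirmatory.

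The order of the list makes this a practical matter. Endpoints 3 and 4 are clinical outcomes for which the documents state no expected effect. Endpoint 5 then returns to the variable on which the trial is powered. If the drug lowers sUA as assumed, endpoint 5 will probably be significant whatever happened at 3 and 4, and its p-value meets the written condition for endpoint 6.

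At stake is the status of endpoints 6 to 9. If SF-36 failed and tender joints succeeded, the written plan would support a confirmatory claim that a strict sequence forbids, and the argument over which reading applies would take place after unblinding.

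The absence of a direction is a separate gap. The primary gate asks for superiority, while the key secondary gate asks only for a small two-sided p-value. A significant worsening in flares at endpoint 8 would therefore open endpoint 9.

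**Working it through.** **Inputs from the documents.** Two-sided level 0.025 per dose; response 45% against 5%; power 90%; 8% early termination; 15 and 20 added patients; about 47 per arm; lower active rate 37% (Protocol 13.1). About 60% with tophi (Protocol 7.2). Nine key secondaries (Protocol 13.4.2).

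**The plan's own figures.** With z = 2.2414 and 1.2816 and mean rate 0.25, the uncorrected n is (2.2414·√0.375 + 1.2816·√0.295)² / 0.40² = 26.7. The continuity correction gives (26.7/4)·[1 + √(1 + 4/(26.7·0.40))]² = 31.5, so **32 per arm**, as stated. Then 32/0.92 = 34.8, so 35; 3 × 35 = 105; 105 + 15 + 20 = 140, or about 47 per arm. These reproduce. The documents state no error rate for the key secondary sequence beyond 0.025 per dose (0.025 + 0.025 = 0.05).

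**Power of endpoint 5.** 0.60 × 47 = 28 per arm. Exact enumeration of the continuity-corrected chi-square test at two-sided 0.025 gives:

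- 45% against 5%: 88.3%
- 37% against 5%: 69.2%

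**Error per dose in the main scenario.** Assume the primary and endpoints 1, 2 and 5 have real effects and 3, 4, 6, 7, 8 and 9 are null. Take independent tests, with the primary, 1 and 2 certain to pass and endpoint 5 passing with probability π. Write p = 0.025 and q = 0.975.

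- *Strict sequence:* a false claim requires a rejection at 3, so the error is 0.025.
- *Literal rule, first part:* a false claim arises if 3 rejects. A rejection at 4 counts only if 3 rejected too, so it adds nothing.
- *Literal rule, endpoints 6–9 when 5 passes:* there is no false claim if 6 does not reject and 8 does not reject together with 7 or 9. That probability is a = q·[1 − p(1 − q²)] = 0.97380.
- *Literal rule, endpoints 6–9 when 5 fails:* there is no false claim if no two neighbours among 6–9 both reject. That probability is b = q⁴ + 4pq³ + 3p²q² = 0.99816.
- *Total:* error = 1 − q·[πa + (1 − π)b].

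| Endpoint 5 power π | Strict | Literal |
|---|---|---|
| 69.2% (37% vs 5%) | 2.5% | 4.3% |
| 88.3% (45% vs 5%) | 2.5% | 4.8% |
| certain | 2.5% | 5.1% |

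**Other scenarios, literal rule, per dose.**

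| Real effects | Error |
|---|---|
| none | 2.5% |
| all except endpoint 3 | 2.5% |
| primary, 1, 2 | 2.8% |
| primary only | 2.9% |
| primary, 1, 2, 5, 7 | 1 − 0.975³ = 7.3% |
| primary, 2, 4, 6, 8 (alternating, worst case) | 1 − 0.975⁵ = 11.9% |

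**Correlation and two doses.** The main scenario was simulated with a shared placebo arm, endpoint 5 certain and 400,000 replicates per setting.

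| Correlation | Per dose, literal | Both doses, literal |
|---|---|---|
| 0 | 5.1% | 9.2% |
| 0.3 | 5.1% | 9.4% |
| 0.5 | 5.0% | 9.2% |
| 0.7 | 4.6% | 8.5% |

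The strict sequence gives about 2.5% per dose and 4.6% to 4.7% over both. These are two-sided rates. Counting only false claims in favour of SEL-212 roughly halves them: at correlation 0.3, 2.5% literal against 1.25% strict per dose.

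**Direction.** With a strongly harmful effect placed at endpoint 3, a strict sequence without a direction condition still gives 2.5% per dose, and about 1.2% for false claims of benefit.

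**The case against.** The strongest reply is that the text describes an ordinary fixed sequence in compressed form. All three places call the procedure hierarchical and say that testing continues from the primary; the estimands are taken in successive order. Protocol 13.4.2 also orders the two flare comparisons, whole treatment before the first three months. Read recursively, the one-step condition is shorthand for all earlier steps. The restart reading is also odd, since endpoint 5 would confer a status on endpoint 6 that it lacks itself. On the intended reading there is no inflation. This stands as evidence of intent. It does not settle the point, because the sentence is the explicit criterion for a confirmatory result and neither document adds a stopping rule.

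The second reply is that the size depends on assumptions. That stands. The documents give no effects for SF-36, tophus response, joints, HAQ-DI or flares, so the scenario behind 4.3% to 5.1% is the reviewer's.

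Three stronger inferences are tempting and not supported:

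- *That the rule doubles the error in general.* It does so only on the literal reading and in some scenarios.
- *That the missing direction drives the inflation.* A strict sequence without a direction condition still holds 2.5%.
- *That the inflation doubles again across two doses.* The two-dose budget is already 5%, so 8.5% to 9.4% is about 1.7 to 1.9 times that budget; the factor does not compound.

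**Conclusion.** The concern holds as a defect in a stated decision rule. As written, the gate allows a sequence broken at endpoint 3 or 4 to restart at 6 through endpoint 5, and the documents' own rates make endpoint 5 likely to pass (69% to 88%).

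The cost in error control is conditional. It requires the literal reading. It also requires that the sUA endpoints work while the other secondaries do not, which is an assumption. In that case the familywise error is about 4.3% to 5.1% per dose against 2.5%, and about 8.5% to 9.4% over both doses against 5%, the two-dose figures taking endpoint 5 as certain to pass. Elsewhere it runs from no inflation to about 12% per dose, and under a strict fixed sequence it is nil.

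The unstated direction is a smaller, independent gap. A reader might infer that the primary result or the sample size is in doubt; neither is affected, because the primary gate requires superiority at 0.025 and the sample size rests on the primary alone. The point should be settled before unblinding.

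**What to change.** Replace the condition in SAP 9.3.1 before unblinding with:

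> Within each dose, the nth key secondary is confirmatory only if the primary and all preceding key secondary main estimands for that dose were significant at two-sided 0.025 in favour of SEL-212; confirmatory testing for that dose stops at the first that is not.

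Align Protocol 13.4.2 and the synopsis at the next amendment. Protocol 13 leaves the details of the statistical methods, including the ordering of the secondaries, to a SAP finalised before database lock, so the SAP change can go first. A protocol amendment needs investigator signature and ethics approval (Protocol 15.3) and need not be raised for this alone.

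With this sentence the error is at most 2.5% per dose and 5% over both doses. Data collection, test methods and sample size do not change. The downside is small: after an early failure, later endpoints lose confirmatory status and are reported as supportive. If a strict sequence was always intended, nothing is lost.
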